CASK trial

Compression After Surgery of the Knee trial

CASK trial, A single-centre, two-arm, controlled, prospective randomized trial comparing standard crepe bandaging with Andoflex TLC Calamine Lite (25-30 mmHg) compression bandaging after knee surgery.

Version 1.1, dd 31 August 2021

Chief Investigator's Statement of Ownership and Content.

I, [name], confirm that this protocol is my work and is owned by me. The protocol conforms with standards outlined in the Declaration of Helsinki 1964.

Name (PRINT):_______
Signature:_____

Date: _____

RESEARCH PROTOCOL SUMMARY

TITLE:	CASK trial, A single-centre, two-arm, controlled, prospective randomized trial comparing standard crepe bandaging with					
	Andoflex TLC Calamine Lite (25-30 mmHg) compression					
Characteria	bandaging after knee surgery.					
Short title:	CASK trial; Compression After Surgery of the Knee trial					
IRAS number	288969					
Device description	AndoFlex TLC Calamine Lite Two-Layer Compression System.					
	Compression of 25-30 mmHg. Layer 1 is a soft foam roll					
	impregnated with calamine that is designed to soothe and					
	calm skin. Layer 2 is a non-latex short stretch compression					
	bandage that sticks to itself and features Easy HandTear					
	Technology, eliminating the need for scissors. It provides a					
	two-step short stretch performance with high working					
	pressure and low resting pressure. Visual indicators are					
	provided for ease of application - ovals become circles when					
	the intended compression is achieved.					
Study type	Medical device trial, involving CE-marked devices used for					
	intended purpose.					
Study design	Single-centre, two-arm, controlled, prospective randomized					
	trial.					
Patient population	Adult participants who have knee surgery – specifically knee replacement or osteotomy - and who meet the study inclusion criteria (including being medically fit to have compression bandaging). Participants must have the capacity to provide informed written consent and complete patient reported outcome measures.					
	The study has the following sample parameters: standard deviation of 2 cm per cohort, power beta of 80%, alpha p-value of 0.05. Sample size takes into account 20% attrition rate, effect size of 0.75 (mean difference of 1.5cm on 10cm visual analogue scale) based on previous ROBOT trial results. Total of 74 patients per surgery type:					
	 37 Patients to receive non-compression bandaging 37 Patient to receive Andoflex TLC Calamine Lite dual-layer compression bandaging 					
	Therefore total is:					
	- 74 knee replacement cases					
	- 74 osteotomy cases					

	Overall trial sample size: 148				
Primary objective	To determine the level of operation-site related pain experienced at day 5 post-operation and to compare the average pain scores of patients in the control and Andoflex TLC Calamine Lite arm respectively, through administration of 10 cm visual descriptor scale (VDS) for 'at rest' pain.				
Secondary objectives	Post-operative patient-reported outcome measures:				
	Prior to surgery and 3, 5, 12 days, and 6 weeks post-surgery - Pain perception, using VDS pain (at rest and walking) and short form McGill pain questionnaire				
	Prior to surgery as baseline, and 6 and 12 weeks post-surgery, knee function and quality of life measurements				
	 Knee and Osteoarthritis Outcome Score (KOOS) Range of motion of the affected limb 				
	Descriptive safety overview at 30 days and 12 weeks post- surgery:				
	 Readmitted to theatre and/or hospital Infection of wound site Diagnosed with pulmonary embolism or deep vein 				
	thrombosis. Patient satisfaction survey at 12 days post-surgery				
Sponsor	North Cumbria Integrated Care NHS Foundation Trust				
Manufacturer & research grant provider	Milliken Healthcare Inc				
Chief Investigator	[name], consultant Orthopaedic Surgeon. North Cumbria Integrated Care NHS Foundation Trust. Phone numbers: [contact] (Secretary); [contact] (office), Email: [contact]				
Co-investigators	[name], consultant Orthopaedic Surgeon. North Cumbria Integrated Care NHS Foundation Trust, [contact]				
	[name], consultant Orthopaedic Surgeon. North Cumbria Integrated Care NHS Foundation Trust, [contact]				

	[name] PhD, Science & Innovation Manager, [contact] or [name]; [contact] North Cumbria Integrated Care NHS Foundation Trust R&D Department, [name] [name], Orthopaedic Specialist Practitioner, North Cumbria University Hospitals NHS Trust, [contact] [name], Advanced Nurse Practitioner, North Cumbria University Hospitals NHS Trust, [contact]
Organisation where research will take place	North Cumbria Integrated Care NHS Foundation Trust Orthopaedics Department [name]
Planned timeline	Recruitment start date (first patient, first visit) 1 July 2021, Recruitment end date (last patient, first visit): 31 July 2022 Recruitment end date (last patient, last visit): 31 Oct 2022
Protocol version, date	Version 1, dd 11May2021

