5.5 Outcome measures

5.5.1 **Primary outcome measures**

To determine the level of operation-site related pain experienced at day 5 post-operation and to compare the average pain scores of patients in the control and Andoflex TLC Calamine Lite arm respectively, through administration of 10 cm visual descriptor scale (VDS) for pain.

The study is powered to detect the established minimal clinically important difference (MCID) of 1.5 cm on a 10 cm VDS pain.

5.5.2 **Secondary outcome measures**

All the outcome measures are summarised in Table 3.

Table 3. Overview of measurements

Weeks	-12 weeks to day of surgery	0 surgery	3 days ^{##}	5 days ^{##}	12 days [#]	6 weeks*	12 weeks *
Application bandage		Х					
straight after surgery							
VDS pain scale (at rest)	Χ		Χ	Χ	Χ	Χ	
VDS pain scale (walking)	Х		Χ	Χ	Χ	X	
McGill pain	Х		Χ	Χ	Χ	X	
questionnaire							
Limb range of motion	Х					X	
KOOS score	Х					X	Χ
Patient satisfaction					Χ	(X, if not	
questionnaire re						returned	
bandaging						yet at 12	
						days)	

^{*} Allowed to be up to 2 weeks early or late # Allowed to be up to 3 days early or late ## Allowed to be up to 1 day early or late

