6. SUBJECTS

6.1 Anticipated number of research subjects

The sample size calculation does take into account a 20% patient attrition rate (withdrawal and loss to follow-up), since this involves a study with multiple time points for data collection up to 12 weeks. Patients will be recruited from the adult (age 18+) population routinely seen by the evaluating clinical staff members. The primary outcome measure is based on knee/leg (ie wound site) pain experienced 5-days post-surgery based on the VDS pain scale 'at rest'. The hypothetical difference in pain perception is 1.5 on a 10 cm scale which equates to a significant 'minimally clinically important difference' for pain (Kelly 2001; Lee et al 2003; Tashjian et al 2009). The values and differences observed in the ROBOT trial will be used for reference.

The non-parametric two-sided Mann-Whitney u-test is applied because the data is ordinal; 80% power and 5% significance is also applied. A priori power calculations using GPower 3.1 software, result in the following sample size summarized in Table 3.

Analysis will be performed on an intention-to-treat basis, although the number of days that a participant has worn a bandage will be recorded.

Data will be analysed as one cohort and also stratified by surgery type (knee replacement, osteotomy) in the resulting analysis.

Table 4, Sample size calculation

	Mean pain score at 5 days post-op	Standard Deviation
Arm A (hypothetical)	5.0	2

Arm B (hypothetical)	3.5	2			
	Power beta of 80%, Alpha p-value of 0.05, Effect size 0.75 Sample size required without any drop-out: 62 samples.				
	Sample size with 20% attrition rate included: 74				
	Total of 74 patients per surgery type:				
	- 37 Patients to receive non-compression bandaging				
	 37 Patient to receive Andoflex TLC Calamine Lite dual-layer compression bandaging 				
	Therefore total is: - 74 knee replacement cases - 74 osteotomy cases				
	Overall trial sample size: 148				

The CONSORT guidelines require a statement on the number of patients assessed for eligibility (Schulz, Altman & Moher 2010). The number of patients screened but who did not meet the inclusion criteria or who declined to participate will be recorded, as will any patients who are lost to follow-up (Appendix 3).

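### The 2 cm SD behind the 80% power per surgery type is not supported by the protocol's own Table 1, which points to about 2.4–3.1 cm and 45–66% power within osteotomy

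*Protocol*

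**What the plan says.** The Research Protocol Summary (patient population) sets a "standard deviation of 2 cm per cohort" and an "effect size of 0.75 (mean difference of 1.5cm on 10cm visual analogue scale) based on previous ROBOT trial results". Section 6.1 adds that "The values and differences observed in the ROBOT trial will be used for reference".

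Table 4 in section 6.1 repeats SD 2 in both arms, with hypothetical means of 5.0 and 3.5 cm. The test is also fixed there: "The non-parametric two-sided Mann-Whitney u-test is applied because the data is ordinal; 80% power and 5% significance is also applied". The result is "Sample size required without any drop-out: 62 samples", raised to 74 for attrition. These 74 are required for each surgery type, which gives 148 overall. Sections 5.5.1 and 8.2 state: "The study is powered to detect the established minimal clinically important difference (MCID) of 1.5 cm on a 10 cm VDS pain".

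Section 2, Table 1 holds the only earlier day-5 data. It reports at-rest pain on a 10 cm scale after osteotomy, 18 patients per arm:

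- Standard care: median 5.5, quartiles 2.5 and 7.0.
- Compression: median 2.5, quartiles 1.5 and 6.5.
- p = 0.068.

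Table 1 gives no SD, and the protocol gives no reason for choosing 2 cm.

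**The concern.** An effect size of 0.75 is 1.5 cm divided by 2 cm, so the SD carries as much of the calculation as the target difference does. Table 1 shows scores spread more widely than an SD of 2 cm would produce. A larger SD shrinks the standardised effect, and 31 patients per arm no longer give 80% power.

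This bears on how the results will be read. Section 4.2 makes a difference in pain outcomes between surgery types a secondary objective, and section 8.3 plans surgery-specific analyses of every outcome. Because Table 4 sizes each surgery type on its own, a null result in one type would be taken as fair evidence against a 1.5 cm effect. At the power Table 1 implies, it would not be.

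**Working it through.** **1. The protocol's own figure.** Inputs from section 6.1: difference 1.5 cm, SD 2 cm, d = 1.5/2 = 0.75, two-sided 5%, 80% power, Mann-Whitney test.

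- A t-test (noncentral t) needs 28.9 per arm.
- Dividing by the Mann-Whitney efficiency 3/π = 0.955 gives 28.9/0.955 = 30.3, so 31 per arm and 62 in total. This matches Table 4.
- Power with 31 per arm is 81%.
- The 74 comes from 62 × 1.2 = 74.4. With 20% loss, 37 × 0.8 = 29.6 per arm remain, and power at SD 2 is 79%. This effect is small.

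**2. Does SD 2 fit Table 1?** Normal data with SD 2 have an interquartile width of 1.349 × 2 = 2.7 cm. Table 1 shows 7.0 − 2.5 = 4.5 and 6.5 − 1.5 = 5.0 cm. In simulated normal samples of 18 with SD 2, a width of at least 4.5 occurred in about 0.4–1.7% of samples and a width of at least 5.0 in about 0.06–0.4%, depending on the quartile convention.

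**3. What SD does Table 1 suggest?** It gives quartiles only, so every SD is a conversion.

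- *From the p-value.* Averaging each arm's three quartile values gives (2.5 + 5.5 + 7.0)/3 = 5.0 and (1.5 + 2.5 + 6.5)/3 = 3.5. Assume the mean difference was therefore 1.5 cm. Two-sided p = 0.068 corresponds to z = 1.825, or t = 1.885 on 34 degrees of freedom. Then SD = 1.5/(1.825 × √(2/18)) = 2.47, or 1.5/(1.885 × √(2/18)) = 2.39. This gives about 2.4–2.5 cm.
- *From the quartiles.* A beta distribution on 0–10 fitted to each arm's quartiles has SD 2.7 (standard care) and 3.1 (compression). The fits are approximate: the fitted quartiles are 2.8/5.0/7.3 and 0.9/3.1/6.2.

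The plausible range is about 2.4–3.1 cm.

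**4. Power for 1.5 cm**, by the method of step 1:

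| SD (cm) | d | 31 per arm | 29.6 per arm | Detectable at 80%, 31 per arm | Whole cohort, 59 per arm |
|---|---|---|---|---|---|
| 2.0 | 0.75 | 81% | 79% | 1.5 cm | 98% |
| 2.4 | 0.63 | 66% | 64% | 1.8 cm | 91% |
| 2.5 | 0.60 | 62% | 60% | 1.9 cm | 88% |
| 2.7 | 0.56 | 56% | 54% | 2.0 cm | 83% |
| 2.9 | 0.52 | 50% | 48% | 2.2 cm | 78% |
| 3.1 | 0.48 | 45% | 43% | 2.3 cm | 72% |

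The whole-cohort column uses 148 × 0.8 / 2 = 59.2, taken as 59 per arm. Its power equals 80% at an SD of about 2.8 cm. Simulated Mann-Whitney tests on bounded 0–10 scores agree: 80% at SD 2 and 58% at SD 2.7 with 31 per arm, and 85% at SD 2.7 with 59 per arm.

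**The case against.** Table 4 labels its inputs hypothetical, and 62 follows correctly from them. The 1.5 cm target is justified separately as an MCID and is not in dispute. The primary objective (section 4.1) concerns knee surgery as a whole, and the power sentence in 5.5.1 and 8.2 does not mention surgery types; at an SD up to about 2.8 cm that sentence holds for the whole cohort. All of this stands, and it limits the point to the SD and to the power per surgery type that Table 4 implies.

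Four stronger readings are tempting, and the protocol does not support them:

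- *SD of 3.3–3.7 cm and power near 34%.* These come from dividing the interquartile widths by 1.349, which assumes unbounded normal data. On a 0–10 scale a flat distribution has SD 2.89 and no single-peaked one exceeds 10/3 = 3.33.
- *The p-value alone rules out SD 2, because a 3.0 cm gap would give z of about 4.5.* That treats a difference in medians as a difference in means, and the compression arm is clearly skewed. With a 1.5 cm mean difference and SD 2, z is 1.5/(2 × √(2/18)) = 2.25.
- *The shortfall is demonstrated for both surgery types.* Table 1 is osteotomy only, with a different compression bandage.
- *Table 1 contradicts the ROBOT results.* The protocol never says that the Table 1 study is the ROBOT trial. The quartile averages equal Table 4's hypothetical means, which suggests a link, but it remains an inference.

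**Conclusion.** The concern holds within these limits. The SD of 2 cm is unexplained and sits badly with the only earlier day-5 data that the protocol shows. No conversion of Table 1 that was tried brings power per surgery type above about 66%.

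For osteotomy, power for 1.5 cm is about 45–66% with 31 evaluable per arm (43–64% after a full 20% loss from 37), against the stated 80%. For the whole cohort it is about 72–91%. A reader might infer that the trial as a whole is underpowered for its primary comparison; that follows only if the SD exceeds about 2.8 cm, which Table 1 neither establishes nor excludes.

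The size rests on three assumptions: a 1.5 cm mean difference behind p = 0.068 for the lower end of the SD range, beta-shaped scores for the upper end, and the same spread for knee replacement as for osteotomy. Each Table 1 arm has only 18 patients, so the range is itself imprecise.

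**What to change.** Keep 148 patients, the endpoint and the test. In the Research Protocol Summary, 5.5.1, 6.1 with Table 4, and 8.2:

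- Replace SD 2 cm with the range implied by Table 1 (about 2.4–3.1 cm), or cite the data that support 2 cm. If such data exist, citing them settles the point.
- State power for 1.5 cm per surgery type as about 45–66% with 31 evaluable per arm, shown for osteotomy and assumed for knee replacement.
- State whole-cohort power as about 72–91% with 59 evaluable per arm, and make the whole-cohort comparison the basis of the power statement, giving the range rather than a flat 80%.
- Do not present each surgery type as having 80% power for the MCID.

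The cost is a change of wording and a less favourable stated power. No extra patients are needed.

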8.2 Primary outcome statistics

To determine the level of operation-site related pain experienced at day 5 post-operation and to compare the average pain scores of patients in the control and Andoflex TLC Calamine Lite arm respectively, through administration of 10 cm visual descriptor scale (VDS) for pain.

Confidential – This document and the information contained herein may not be reproduced, used or disclosed without written permission from North Cumbria Integrated Care NHS Foundation Trust Page | 18

The study is powered to detect the established minimal clinically important difference (MCID) of 1.5 cm on a 10 cm VDS pain.

The average difference between time points will be calculated per group, 5 days post-surgery weeks being the primary endpoint. Three days, 12 days and 6 weeks post-surgery will also be analysed. To compare the groups, the Mann-Whitney U-test will be applied.

To avoid relying on one outcome measure related to pain, at 3, 5, 12 days, and 6 weeks post-surgery pain perception will also be measured using the short form McGill pain questionnaire. Again, to compare groups the Mann-Whitney U-test will be applied.

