8.3 Secondary outcome statistics

The average baseline demographics for participants in each group will be compared to ascertain that randomisation has indeed led to comparable distribution of participants:

Sex, age, height, weight, BMI, length of stay, type of anaesthetic for surgery and type of analgesics post-surgery.

To compare outcomes between the two groups (standard vs Andoflex TLC Calamine Lite bandaging), student t-test, Mann-Whitney U-test or Chi-squared test will be applied as applicable, depending on type and distribution of data .

Cox proportional hazards regression analysis will be conducted to investigate the role of bandaging and other covariates (as mentioned above) in post-surgery related pain and knee function.

The statistics apply to:

Up to 12 weeks prior to surgery, and 12 weeks post-surgery, knee function and quality of life measurements: Knee and Osteoarthritis Outcome Score (KOOS), and range of movement of the affected limb (goniometer)

Descriptive safety overview at 30 days and 12 weeks post-surgery:

- Readmitted to theatre and/or hospital
- Infection of wound site
- Diagnosed with pulmonary embolism or deep vein thrombosis
- All monitored remotely by review of patients' hospital notes.

Patient satisfaction survey at 12 days post-surgery – any difference in outcome will be determined with Mann-Whitney U-test

For all outcome measures and statistics, both whole cohort and surgery-specific stratification analysis will be conducted.

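### Section 8.3 does not name the 6-week KOOS among its analysed time points, and no stated KOOS analysis uses the baseline score

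*Protocol*

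**What the plan says.** The protocol states the KOOS time points in three places.

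- **Summary, secondary objectives:** "Prior to surgery as baseline, and 6 and 12 weeks post-surgery, knee function and quality of life measurements". KOOS and range of motion are both listed under this line.
- **Section 5.5.2** ("Table 3. Overview of measurements"): the KOOS row is marked at baseline, 6 weeks and 12 weeks. The range-of-motion row is marked at baseline and 6 weeks only.
- **Section 8.3**, in the list of what its statistics apply to: "Up to 12 weeks prior to surgery, and 12 weeks post-surgery, knee function and quality of life measurements". KOOS and range of movement follow. Six weeks does not appear.

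For method, section 8.3 says of the two-arm comparison that "student t-test, Mann-Whitney U-test or Chi-squared test will be applied as applicable, depending on type and distribution of data". It then adds a regression whose second target, after pain, is the function of the knee: "Cox proportional hazards regression analysis will be conducted to investigate the role of bandaging and other covariates (as mentioned above) in post-surgery related pain and" (sentence cut short here). The covariates it points back to are "Sex, age, height, weight, BMI, length of stay, type of anaesthetic for surgery and type of analgesics post-surgery". Baseline KOOS is not one of them. The section closes with a general statement: "For all outcome measures and statistics, both whole cohort and surgery-specific stratification analysis will be conducted".

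**The concern.** Section 4.2 asks whether the compression bandage improves patient-reported outcomes, including knee function, and KOOS is the instrument for that. The protocol's own analysis section gives a list of time points that differs from its measurement schedule, and the visit it omits is the one closer to the 5-day bandage period. If this stays unresolved, whether the 6-week KOOS counts as a planned comparison can be decided after the data are seen.

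The second issue is use of the data. Baseline KOOS is scheduled for every patient, yet none of the named analyses takes it in. The trial was sized on day-5 pain and not on KOOS, so precision on KOOS is worth having where it costs nothing.

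**Working it through.** **Time points side by side**

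| Source | KOOS | Range of motion |
|---|---|---|
| Summary | baseline, 6 wk, 12 wk | baseline, 6 wk, 12 wk |
| Table 3 (5.5.2) | baseline, 6 wk, 12 wk | baseline, 6 wk |
| Section 8.3 | pre-surgery, 12 wk | pre-surgery, 12 wk |

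For KOOS, two sources agree and section 8.3 differs. For range of motion all three differ, and section 8.3 applies its statistics at a visit where Table 3 takes no measurement.

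**Does any stated analysis use baseline KOOS?**

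- The t-test, Mann-Whitney and chi-squared tests take no covariate.
- The Cox model takes covariates, but its list omits baseline KOOS. It also needs a time to an event, and the protocol defines no event for a KOOS score.
- A difference between time points is stated once: "The average difference between time points will be calculated per group, 5 days post-surgery weeks being the primary endpoint". That is in section 8.2, under pain, and not for KOOS.

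**The plan's own sample-size figure.** Section 6.1 gives 62 per surgery type before drop-out, for day-5 pain with effect size 0.75. A two-sided 5% Mann-Whitney test (t-test power with efficiency 3/π = 0.955) has power 0.796 at 30 per arm and 0.810 at 31. That gives 31 per arm, or 62, as stated. Attrition: 62 × 1.2 = 74.4, matching the stated 74. The protocol gives no KOOS standard deviation, target difference or baseline correlation.

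**Evaluable number for KOOS.** 148 × (1 − 0.20) = 118.4, about 59 per arm. (Using 62 per arm would mean 124 of 148 retained, a 16% loss and not the stated 20%.)

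**Gain from adjustment.** Relative to the unadjusted comparison, the variance of the baseline-adjusted difference is 1 − r², where r is the correlation of baseline with follow-up KOOS. I assume r between 0.3 and 0.6.

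- r = 0.3: 1 − 0.09 = 0.91, a 9% cut.
- r = 0.6: 1 − 0.36 = 0.64, a 36% cut.

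Detectable difference, 80% power, two-sided 5%, 59 per arm:

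- Normal approximation, unadjusted: (1.960 + 0.842) × √(2/59) = 0.516 SD. The noncentral t gives 0.520 SD.
- Adjusted, r = 0.3: 0.520 × √0.91 = 0.496 SD.
- Adjusted, r = 0.6: 0.520 × √0.64 = 0.416 SD.

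Within one surgery type (74 × 0.8 = 59.2, about 29.5 per arm), the normal approximation gives 0.73 SD unadjusted. It falls to 0.70 SD at r = 0.3 and to 0.729 × 0.8 = 0.58 SD at r = 0.6.

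**If a change score were meant.** Its relative variance is 2(1 − r): 1.40 at r = 0.3, 1.00 at r = 0.5 and 0.80 at r = 0.6. Baseline adjustment gives 0.91, 0.75 and 0.64, so it is more precise throughout this range.

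**The case against.** Several points on the other side stand.

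- **Baseline is listed.** A reader might infer that KOOS is analysed at 12 weeks alone. Section 8.3 also names the pre-surgery score, though without saying how it is used. Listing before and after together is compatible with a change score.
- **Week 6 may be covered.** A reader might infer that the 6-week KOOS has no planned analysis at all. The general sentences in section 8.3, on comparing outcomes between groups and on all outcome measures, can be read to include it. They name no visit, however, and the one line that assigns KOOS time points omits week 6. What the text supports is that the visit is not named.
- **A covariate model exists.** It would be wrong to say that only two-sample tests are planned, since a Cox regression is aimed at knee function. It does not fill the gap, for the reasons shown in the working.
- **The unadjusted test is valid.** A reader might infer that chance imbalance in baseline KOOS biases the 12-week result. Under randomisation it does not, because the standard error already allows for such imbalance. The loss is in precision.
- **A statistical analysis plan may settle the method.** Section 8.3 leaves test choice open, and adjustment of a secondary outcome is often specified later. This weakens the adjustment point, which is an improvement and not the correction of an error. It does not touch the mismatch in time points, which lies within the protocol itself.

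**Conclusion.** The concern holds in limited form. The documentary defect needs no assumption: section 8.3 omits the 6-week KOOS that the summary and Table 3 schedule, and range of motion is inconsistent across all three places.

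As stated, neither the two-sample comparison nor the Cox regression uses baseline KOOS, and Cox regression is unsuited to a score outcome. The cost is modest: about 0.52 SD detectable against about 0.50-0.42 SD with adjustment. That range rests on an assumed correlation of 0.3 to 0.6, on the stated 20% attrition applying to KOOS, and on a comparison of means. A correlation outside the range would change the gain.

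The documents do not support saying that the KOOS comparison is biased or that the 6-week score will go unanalysed. KOOS and range of motion are secondary outcomes, and the primary analysis is unaffected.

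**What to change.** In section 8.3:

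1. List KOOS at 6 and 12 weeks, to match the summary and Table 3.
2. For KOOS, replace the two-sample test and the Cox regression with a linear model of KOOS on arm, baseline KOOS and surgery type (section 6.1.1 randomises per surgery type). Report the adjusted mean difference with its 95% confidence interval at each visit. In the surgery-specific analyses, drop the surgery-type term.
3. Reconcile the range-of-motion time points across the summary, Table 3 and section 8.3.

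Naming one visit as the lead KOOS time point, or fitting both visits in one model with an arm-by-visit term, is optional.

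For KOOS the cost is a change of wording and a standard regression with a check of residuals. It needs no new data and no more patients. For range of motion, the cost depends on which schedule the sponsor confirms: keeping 12 weeks would add a measurement that Table 3 does not now include.
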